TITLE: The impact of suctioning on oxygenation during RSI in the Emergency Department – A Multi-centre Pilot Study

Unique Protocol ID: 2020-01-32

Document Date: January 2, 2020

Introduction

Rapid Sequence Intubation (RSI) is a common procedure in Emergency Departments (ED). However, it is a high-risk procedure and has been associated with significant complications including hypoxia, hypotension, airway trauma, aspiration, and death (1-3). Specifically, hypoxic episodes during intubation can lead to poor outcomes such as dysrhythmias, haemodynamic compromise, hypoxic brain injury and cardiac arrest, and is therefore of primary concern during any intubation procedure (4,5). Aspiration is a serious adverse event and potential cause of hypoxia during RSI and can lead to poor patient outcomes downstream of the procedure. The reported incidence of aspiration during RSI in the ED ranges from 3 to 8% in the ED population (6,7). In order to achieve an optimal view of the glottis and prevent pulmonary aspiration of fluids in the oropharynx, providers apply suction prior to and during laryngoscopy, using a Yankauer or large bore suction catheter. (8).

There is currently significant variation in suctioning during laryngoscopy, with some providers using very little suction as needed to clear heavy fluids (judicious suctioning), while others utilise suction aggressively (lead with suction) and as a part of their routine laryngoscopy technique (9, 10, 11). Evidence suggests inline suction on already-intubated patients accelerates desaturation, but we are aware of no studies examining the impact suctioning has on the speed of desaturation during emergent endotracheal intubation (11,12).

This pilot study aims to compare the effects of intermittent, as-needed “judicious” suctioning versus aggressive “continuous” (lead with) suctioning on oxygenation during rapid sequence intubation in the emergency department.

Methods

Setting

In order to enrol patients into this pilot study and to gain experience from International centres this study will be performed at 4 sites: the Royal Prince Alfred (RPA) Hospital Emergency Department, Sydney, Australia, Mount Sinai Hospital, Manhattan, NY, Maimonides Medical Center, Brooklyn, NY and NYC H+H/Lincoln Medical Centre, Bronx, New York, USA. The RPA Hospital is a Level 1 Trauma Centre with approximately 85,000 presentations and 240 intubations per year. Lincoln Medical Centre is a Level 1 Trauma Hospital with approximately 175,000 presentations and 450 intubations per year. Mount Sinai Hospital is a tertiary referral center whose ED sees approximately 125,000 patients per year with around 200 intubations. Maimonides Medical Center is a level 1 trauma center that treats about XXX and performs about XXX intubations per year.

Study Participants

All adult patients requiring emergent rapid sequence intubation (RSI) in the resuscitation bay will be included in the study. Patients that have a heavily soiled airway (i.e. secretions, vomitus, blood) as deemed by the physician requiring suction will be excluded.

Variables measured

The variables included in the study are shown on the Data collection sheet (Appendix 3) and will include the following:

- Patient details: Age, Gender, estimated weight
- Indication for RSI
- C-spine immobilisation and manual inline stabilisation
- Method of preoxygenation
- Method of apnoeic oxygenation, if performed
- Head up or supine position
- Oxygen saturation and ETO₂ prior to starting preoxygenation and at induction (completion of preoxygenation)
- Oxygen saturation and ETO₂ during procedure (at 10 second intervals starting with induction).
- Time of preoxygenation
- Induction medication and dose used
- Paralytic and dose used
- Induction time
- Endotracheal intubation time
- Method of intubation
- Number of attempts
- Cormack-Lehane grade of airway
- Use of cricoid or External laryngeal manipulation
- Continuous versus judicious suctioning

Intervention

The aim of this study is to investigate the effect of suctioning (a current technique used conventionally in RSI) on oxygenation levels during RSI. This being noted, there is no new intervention being applied to the patient.

In order to investigate this, the current standard of care of suctioning will be used either by judicious means (i.e. in and out suction as needed) or continuous means (i.e. throughout the procedure, including laryngoscopy and tube placement) according to conventional practice at the discretion of the treating physician. For all patients involved in the study, there will be no new intervention applied. The impact of the use of suctioning, again which is standard of care and applied by convention, will be determined by measuring oxygen saturation as a primary outcome. All aspects of RSI will be at the discretion of the treating clinician, which is the current standard, including induction/relaxant medication, positioning of the patient, preoxygenation method, method of intubation and post-intubation sedation. At all institutions RSI is performed in a similar manner utilising an airway checklist (Appendix 1 and 2). However, there are no 'Standard Operating Procedures' for RSI in any ED and therefore intubation technique will vary depending on clinician preference and the clinical circumstances.

Once the decision to perform RSI has been made by the treating team, the patient will be enrolled into either a judicious or continuous suction group at random. In either case, suctioning will be applied to the patient as determined necessary by the clinician. Rapid sequence intubation will then be performed in the standard means by the treating provider.

Outcomes

Primary Outcome

The primary outcome of this study is the oxygen saturation achieved (SpO_2) at the time of tube placement (via confirmation with first ETCO_2 waveform) achieved during the intubation period.

Secondary Outcomes

The secondary outcomes measured include:

- Incidence of desaturation ($\text{SaO}_2 < 90\%$) or > 10 points from baseline during the intubation period
- Lowest O_2 saturations at any point during the intubation period
- The ETO_2 at induction and at ETT confirmation.
- Time from preoxygenation to endotracheal intubation
- Complications during RSI: bradycardia, tachycardia, hypotension, hypertension, oesophageal intubation, aspiration, airway or dental trauma, equipment or medication error
- Number of intubation attempts

Data Collection

The data will be collected prospectively during the time of RSI by nursing and medical staff with the use of a data collection sheet (Appendix 3). Staff at RPA ED are familiar with the data collection sheets as prior studies in relation to RSI have been performed previously (Study number Re: X12- 0394). Similarly staff at Lincoln Medical centre and Mount Sinai perform routine data collection on all RSI's performed in the ED for quality improvement purposes. The staff at Maimonides and Mount Sinai will be trained in the procedure for collecting data with the use of the data collection sheets.

Patient risk

This study investigates the effect of providing suction during RSI on SpO₂ levels. This study will have no direct impact on patient care as it evaluates the use of a current accepted standard in the ED. This adds to clinical information and may lead to either no change or improved patient care. There are no risks to the patient as the patient will be receiving standard of care in both arms of the study. Patients will be critically ill requiring an emergency procedure and therefore, consent is not necessary for this study as per the criteria of the Common Rule for waiver of informed consent for emergency research.

Sample Size

A sample size calculation for this study is not possible as this is a pilot study and there is currently no reported data on the impact suctioning has on oxygen saturation during RSI in emergency department patients. For this reason we have decided to perform a convenience sample of 100 patients (50 in the judicious group and 50 in the continuous group). Data from this study will be used to provide statistics for a sample size and power calculation for a larger randomized control trial in the future.

Statistical Analysis

Descriptive statistics will be used for the cohorts. Means with 95% confidence intervals and medians with interquartile range will be used to describe the cohorts. Chi squared test will be used to compare the proportion of patients that experience desaturation between the cohorts. A simple student's t-test will be used to compare the mean oxygen saturations and end tidal oxygen levels measured between the cohorts.

Study Endpoints

The endpoint for this pilot study will be the enrollment of 50 patients in each group to a total of 100 patients.

References

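### Could the heavily-soiled-airway exclusion be applied after random allocation and so bias the comparison?

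*Combined protocol and SAP*

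**What the plan says.** Study Participants sets eligibility in two adjacent sentences. The first is "All adult patients requiring emergent rapid sequence intubation (RSI) in the resuscitation bay will be included in the study". The second is "Patients that have a heavily soiled airway (i.e. secretions, vomitus, blood) as deemed by the physician requiring suction will be excluded". Neither gives a time point.

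The Intervention section places random allocation next, with intubation afterwards: "Once the decision to perform RSI has been made by the treating team, the patient will be enrolled into either a judicious or continuous suction". It defines the arms by how suction is used: in and out when needed, or running for the whole procedure, including laryngoscopy and tube placement. It adds: "In either case, suctioning will be applied to the patient as determined necessary by the clinician".

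Sample Size sets a convenience sample without a power calculation and gives its purpose: "Data from this study will be used to provide statistics for a sample size and power calculation for a larger randomized control trial". Study Endpoints says: "The endpoint for this pilot study will be the enrollment of 50 patients in each group to a total of 100 patients". Statistical Analysis compares the two cohorts by t-test and chi-squared test and does not define which patients form them. Appendices 1 to 3 (airway checklists and data collection sheet) are cited but are not in the text available for this review.

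**The concern.** Three features together look like a weakness.

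- **Timing.** Laryngoscopy comes after allocation, so soiling first seen then is seen by a physician who already knows the arm.
- **Overlap with the treatment.** The exclusion depends on a judgement that suction is required. The Introduction describes judicious suction as sparing use to remove heavy fluid, and the Intervention section leaves suction in both groups to clinical judgement of need. One finding could be read as a reason to exclude or as an occasion to use the assigned technique.
- **No backstop.** No analysis population is named, and it is not stated whether the target of 50 per group counts allocated or retained patients.

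If soiled patients were removed after allocation at different rates by arm, the groups would no longer be comparable by randomisation. A distorted difference could then pass into the sizing of the later trial. The documents do not indicate the direction of any such distortion.

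**Working it through.** **1. The text.** The stated order is: decision to perform RSI, random allocation, intubation. The exclusion stands outside that sequence, in the section that defines who is in the study, and concerns patients who have a soiled airway. No section describes withdrawing, dropping or replacing an allocated patient. For harm to arise, four things must all happen:

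- soiling is recognised only after allocation;
- the physician treats it as an exclusion;
- this happens more in one arm than in the other;
- the analysts leave those patients out.

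The wording rules out none of these, but the plan calls for none of them.

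The overlap is also narrower than it looks. The arms vary the manner of suction, not the need for it, and the criterion requires a heavily soiled airway, not merely some need for suction. The remark about heavy fluid describes current practice in the Introduction; it is not the arm definition.

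**2. Size if the criterion were misapplied.** The plan's only figure is 50 + 50 = 100, which agrees. It states no alpha, power, effect or SD, so every input below is an assumption: share soiled p = 0.10 to 0.30; SpO2 difference of soiled patients d = 0.5 to 1.0 within-stratum SD; fraction f of soiled patients dropped from an arm.

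Soiled share remaining in an arm: q(f) = p(1 − f)/(1 − pf). Bias = d × [q(f_A) − q(f_B)].

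| Dropped, arm A v arm B | p = 0.10, d = 0.5 | p = 0.30, d = 1.0 | False-positive rate |
|---|---|---|---|
| Same fraction in both | 0 | 0 | 5.0% |
| Quarter v half | 0.5 × (0.0769 − 0.0526) = 0.012 | 0.2432 − 0.1765 = 0.067 | 5.0–6.1% |
| None v half | 0.5 × (0.1000 − 0.0526) = 0.024 | 0.3000 − 0.1765 = 0.124 | 5.2–8.7% |
| None v all | 0.5 × 0.10 = 0.05 | 1.0 × 0.30 = 0.30 | 5.7–29% |

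The false-positive rate is for a two-sided 5% t-test on 98 degrees of freedom with 50 analysed per arm. The non-centrality is bias/√[(v_A + v_B)/50], with v = 1 + q(1 − q)d². For none v half at the upper end, v_A = 1.21 and v_B = 1.145, so 0.124/√(2.355/50) = 0.57, giving 8.7% (8.4% if the 7.5 dropped patients are not replaced). For none v all, v_A = 1.21 and v_B = 1, so 0.30/√(2.21/50) = 1.43, giving 29%.

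**3. Carry-over to the later trial.** Assume a true difference of 0.5 SD, 80% power and two-sided 5%: 64 per arm.

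- A planning value off by 0.024 SD gives 59 or 71.
- Off by 0.124 SD gives 42 or 112 (113 if the effect is rounded to 0.376). With 42 per arm, power at 0.5 SD is 62%.
- In total-SD units the upper bias is 0.124/1.085 = 0.114, where 1.085 = √[(1.21 + 1.145)/2]. That gives 43 or 107.
- Sampling error alone: the standard error is √(2/50) = 0.2 SD, and the 95% half-width is 1.98 × 0.2 = 0.40 SD. One standard error either side of 0.5 gives 34 or 176.

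Ordinary sampling error in a pilot of this size moves the later sample size more than the hypothetical bias does. Sample Size also says only that the pilot will supply statistics; it does not commit to using the observed difference as the planning effect.

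**The case for a change.** The strongest case for a change is that the protection rests on convention and not on text. Four sites take part, and the Intervention section says none has a standard operating procedure for RSI, so sites might apply the criterion at different moments. The listed variables include no item for soiling or exclusion. If patients were dropped and replaced, a final 50 and 50 would hide it, and it could not be reconstructed afterwards. With suction already running in the continuous arm, need might be judged differently there. If every soiled patient were lost from one arm, the bias would reach 0.30 SD, which is not small. The remedy would cost a sentence or two.

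What stands is that the timing and the analysis set are unwritten, and that writing them down would do no harm. What does not stand is the step from silence to a flawed comparison. An eligibility criterion need not say that it precedes enrolment. The variable list says what the data will include and is not shown to be complete, and the unseen data sheet may record eligibility. The 0.30 SD case needs complete removal in one arm and none in the other, which nothing in the document suggests.

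**Conclusion.** No change is called for. On the ordinary reading the physician judges soiling as part of eligibility, eligible patients are allocated, and everyone allocated is compared in the assigned group. The bias from this criterion is then zero. The silence on timing and analysis set is missing detail that a competent analyst fills in that way. Leaving out heavily soiled airways when comparing styles of suction is a coherent design choice.

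This rests on two things: that sites apply the criterion before allocation, and that soiling found later is not used to remove patients. If either failed, the damage would depend on how unequally the arms were affected. Under the partial-loss assumptions above it is 0.012 to 0.124 SD, against a standard error of 0.2 SD. The documents contain nothing from which to estimate it, and nothing to suggest that it is planned or likely.

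The Intervention section also says that suction style follows the treating physician's discretion while groups are assigned at random. That is a separate question and is not settled here.

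### Allocation generally comes before preoxygenation, which is left to a clinician who knows the arm, so a difference in SpO2 at tube placement cannot be attributed cleanly to suction.

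*Combined protocol and SAP*

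**What the plan says.** All references are to the combined protocol and SAP.

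- **Time of allocation (Methods, Intervention):** "Once the decision to perform RSI has been made by the treating team, the patient will be enrolled into either" one of the two suction groups, chosen at random. The next step but one reads "Rapid sequence intubation will then be performed in the standard means by the treating provider." No randomisation mechanism, concealment or blinding is described.
- **Discretion (same section):** "All aspects of RSI will be at the discretion of the treating clinician, which is the current standard." The list of what this covers reads "including induction/relaxant medication, positioning of the patient, preoxygenation method, method of intubation and post-intubation sedation." The section also states that "there are no 'Standard Operating Procedures' for RSI in any ED and therefore intubation technique will vary depending on clinician preference."
- **Primary outcome (Outcomes):** the SpO2 level at tube placement, timed by the first ETCO2 waveform. It is a level and not a change from induction.
- **Analysis (Statistical Analysis):** mean saturations and end-tidal oxygen are compared by Student's t-test. No covariate is named.
- **What is recorded (Variables measured):** preoxygenation method and time, apnoeic oxygenation, position, and SpO2 and ETO2 both before preoxygenation and "at induction (completion of preoxygenation"), then every 10 seconds. ETO2 at induction is also a secondary outcome.

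**The concern.** The stated aim is the effect of suction technique on oxygenation. Oxygen reserve at the end of preoxygenation is an obvious influence on SpO2 at tube placement. Here that reserve is built up mostly after the arm is known, by someone free to vary how it is done.

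If preoxygenation differs between arms because the arm is known, the difference enters the primary comparison and is read as a suction effect, or hides one. ETO2 at induction and the time from preoxygenation to intubation are exposed in the same way.

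Adjustment after the fact is not a clean repair. Under the present order, SpO2 and ETO2 at induction are post-allocation values, so conditioning on them is not baseline adjustment. The pilot's data are also meant to supply the sample size calculation for a larger trial. A distorted difference would pass into that calculation, and the allocation procedure may be copied.

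**Working it through.** **1. Order of events.** Allocation follows the decision to perform RSI, and RSI is performed after that. Preoxygenation method is listed as an aspect of RSI. So preoxygenation generally follows allocation. This is an inference: the plan does not fix the moment, and a patient may already be on oxygen when the decision is made.

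**2. Knowledge of the arm.** The operator delivers the assigned technique and no blinding is described. So the arm is known to the operator by laryngoscopy at the latest, and nothing keeps it from the team before then.

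**3. The plan's own figure.** The only figure to check is 50 + 50 = 100, which agrees. No alpha, power, effect size or SD is given, so everything below uses assumed values.

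**4. Possible shift in arm means.** Shift = (share of one arm whose approach changes) × (SpO2 points that the change is worth).
- Low: 0.10 × 3 = 0.3 points.
- High: 0.30 × 8 = 2.4 points.

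**5. Effect on the planned t-test.** Assume 50 per arm, two-sided alpha 0.05, no suction effect, and a shift that carries through in full to tube placement. The standard error of the difference is SD × √(2/50) = 0.20 × SD. The noncentrality is shift / (0.20 × SD), with 98 degrees of freedom and critical value 1.984. For example, with SD 8 and shift 2.4: 2.4 / 1.6 = 1.5, giving a rejection rate of 32%.

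| Shift (points) | SD 5 | SD 8 | SD 10 |
|---|---|---|---|
| 0.3 | 6% | 5% | 5% |
| 1 | 17% | 9% | 8% |
| 2 | 51% | 24% | 17% |
| 2.4 | 66% | 32% | 22% |

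The nominal rate is 5%.

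**6. Effect of moving the disclosure.** In 10,000 simulated trials per setting (assumed SD 5 at induction and SD 6 for the later fall, no suction effect), allocation known before preoxygenation gave:
- a shift of 1 point: 9% rejections, mean difference about 1;
- a shift of 2 points: 25% rejections, mean difference about 2.

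With the arm disclosed after preoxygenation, rejections stayed between 4.6% and 5.0% and the mean difference stayed near 0.

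**7. Side benefit of the covariate.** Under the same assumed SDs, the total SD is √(5² + 6²) = 7.8. The unadjusted standard error is 0.20 × 7.8 = 1.56 points. Adjusting for SpO2 at induction leaves about 0.20 × 6 = 1.20 points.

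SpO2 cannot exceed 100%, so a real shift may not carry through in full. Steps 5 to 7 are illustrations, not predictions.

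**The case against.** **Clinicians have not been shown to compensate.** This stands. The Introduction reports faster desaturation only for in-line suction in patients who already have a tube. It says the authors know of no study in emergency intubation, and that some providers lead with suction routinely. A reader might infer that the plan itself gives clinicians a reason to preoxygenate the continuous arm more. That is plausible but not documented.

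**The direction is not established.** This stands too. Extra preoxygenation in the continuous arm would raise SpO2 there. It could mask an accelerating effect of suction but could not create one. A false accelerating effect would need behaviour in the opposite direction, for which the documents offer no reason.

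**Suction may start before laryngoscopy.** The Introduction describes suction before as well as during laryngoscopy, and continuous suction is defined as lasting throughout the procedure. So it cannot be said that the arms differ only from laryngoscopy onward. The proposed disclosure therefore has to precede any study suction.

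**Safeguards exist.** Preoxygenation variables are recorded and ETO2 at induction is compared between groups, so a difference could be seen. That allows detection, not repair, and the analysis does not use these values.

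**Randomisation still protects the comparison.** Correct for the assigned strategies under usual care. What weakens is the claim that suction caused the difference, and that claim is the study's aim.

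**Other matters come first.** The same section leaves the choice of suction to the physician while allocating it at random. Those statements must be reconciled, but that is a separate point and does not remove this one.

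**Conclusion.** The concern holds as a weakness of attribution. The plan allows preoxygenation to differ by arm after allocation, and the primary analysis would pass any such difference through unadjusted. It does not show that this will happen, in which direction, or by how much.

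A reader might infer that the result will be biased, or that the randomised comparison is invalid. The documents support neither. The 0.3 to 2.4 point range is assumed throughout: at the low end the false-positive rate stays at 5% to 6%, and at the high end it is 22% to 66% for SDs of 10 down to 5.

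The conclusion rests on two close inferences: that preoxygenation generally follows allocation, and that the treating team knows the arm. The change is worth making because it costs little and closes this route by design.

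**What to change.** In Methods, Intervention, state something like: *Eligibility is confirmed, and the SpO2 and ETO2 at the end of preoxygenation, the preoxygenation method, the patient's position and the planned use of apnoeic oxygenation are recorded, before the allocation is disclosed to the treating team. Disclosure follows that recording and precedes laryngoscopy and any study suction.*

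In Statistical Analysis, prespecify SpO2 at induction as a baseline covariate for the primary comparison (for example, analysis of covariance). It is then a true pre-disclosure value. ETO2 at induction becomes a baseline characteristic and should no longer be listed as an outcome.

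**Cost.** One extra step shortly before induction in critically ill patients. There are no extra patients, and the measurements are already collected; only the planned use of apnoeic oxygenation must be noted in advance. The plan describes no allocation mechanism, so one must be specified in any case. The checklists and data sheet in the appendices are not in the text available here, so fit with workflow could not be checked.

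**Residual limit.** Position, device and apnoeic oxygenation can still change after disclosure. Report such changes by arm.

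### Suction technique is both left to the physician and assigned at random, and the analysis does not say whether groups are compared as assigned or as received

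*Combined protocol and SAP*

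**What the plan says.** The Intervention section makes three statements about how a patient comes to receive a technique.

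- Choice by the physician: one of the two techniques is used "according to conventional practice at the discretion of the treating physician".
- Choice by chance: once RSI has been decided on, "the patient will be enrolled into either a judicious or continuous suction group at random".
- Delivery: "In either case, suctioning will be applied to the patient as determined necessary by the clinician".

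The same section defines the techniques as "judicious means (i.e. in and out suction as needed" and "continuous means (i.e. throughout the procedure, including laryngoscopy and tube placement". The Introduction describes current practice as varying between clinicians, "with some providers using very little suction as needed to clear heavy fluids (judicious suctioning" and others suctioning aggressively as routine.

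Study Participants excludes patients with a heavily soiled airway "as deemed by the physician requiring suction will be excluded", with no timing relative to allocation. Variables measured has a single item for continuous versus judicious suctioning. It refers to the form in these words: "The variables included in the study are shown on the Data collection sheet (Appendix 3". That appendix is not in the available text.

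Statistical Analysis compares *cohorts* by a chi-squared test (desaturation) and a Student's t-test (oxygen saturation and end-tidal oxygen). It does not define the cohorts, and no section names an intention-to-treat, per-protocol or as-treated population. Sample Size sets 50 per group, with no power basis, and says the data will inform the sample size of a later randomised trial.

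**The concern.** No sentence says which rule of choice governs, and none requires the clinician to deliver the assigned technique. Taken literally, the delivery sentence lets a continuous-arm patient receive as-needed suction and still comply with the protocol. Four sites in two countries must apply this text, and the protocol says none has a standard operating procedure for RSI.

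Three different studies could result.

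1. Randomised, compared as assigned: a valid comparison, but a diluted one if continuous suction is not enforced.
2. Randomised, grouped by suction received: the protection of randomisation is partly lost.
3. Technique chosen by the physician: the unadjusted tests are open to confounding by provider habit, site and residual indication. The soiled-airway exclusion reduces only the last of these.

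The result of this pilot is meant to feed a later trial's sample size, so a diluted or confounded difference would carry forward.

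**Working it through.** **Inputs.** From the documents: 50 per group, 100 in total (50 + 50 = 100, which agrees). The plan has no power calculation to reproduce and gives no SD, effect size, alpha or switching rate. Everything else below is assumed: two-sided 5% tests, SD 8 saturation points (range 6 to 10), and the prevalences and choice rates shown.

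**A. Randomised, compared as assigned: dilution.** Suppose a share c of the continuous arm receives as-needed suction and then has the judicious arm's mean. The as-assigned difference is (1 − c) times the true difference. By the normal approximation, the difference with 80% power is (1.960 + 0.842) × √(2/50) = 0.560 SD. Power after dilution is Φ(2.802 × (1 − c) − 1.960).

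| c | Difference (SD) | Power | Sample-size factor 1/(1 − c)² |
|---|---|---|---|
| 0 | 0.560 | 80% | 1.00 |
| 10% | 0.504 | 71% | 1.23 |
| 20% | 0.448 | 61% | 1.56 |
| 30% | 0.392 | 50% | 2.04 |

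The last column is the factor by which a later trial's size grows if it is planned on the diluted difference.

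**B. Randomised, grouped by suction received.** Let 15% of patients have a feature that lowers SpO2 by 5 points. In the continuous arm, 5% of those with the feature and 20% of those without it receive as-needed suction.

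- Received continuous, as shares of all patients: 0.5 × 0.15 × 0.95 = 0.071 with the feature, 0.5 × 0.85 × 0.80 = 0.340 without. Feature share: 0.071/0.411 = 0.173.
- Received judicious: 0.5 × 0.15 × 1.05 = 0.079 with, 0.5 × 0.85 × 1.20 = 0.510 without. Feature share: 0.079/0.589 = 0.134.
- Bias: 5 × (0.173 − 0.134) = 0.20 points, with expected groups of 41 and 59.
- With 30% drift among those without the feature, the shares are 0.193 and 0.125, the bias is 0.34 points, and the groups are 37 and 63.

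**C. Physician chooses.**

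- *Indication:* same feature, with continuous suction chosen in 70% of those who have it and 40% of the others. Feature share under continuous: 0.15 × 0.7/(0.15 × 0.7 + 0.85 × 0.4) = 0.236. Under judicious: 0.15 × 0.3/(0.15 × 0.3 + 0.85 × 0.6) = 0.081. Bias: 5 × 0.155 = 0.77 points. Over prevalence 10 to 30%, choice 60 to 80% versus 40%, and effect 3 or 5 points, it runs from 0.22 to 1.68.
- *Provider or site:* half the patients under providers or sites with mean SpO2 2 points lower, and continuous use of 70% versus 30%. Bias: 2 × (0.7 − 0.3) = 0.8 points (0.4 at 60/40, 1.2 at 80/20).

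**Scale.** The 95% confidence-interval half-width is t(0.975, 98 df) × SD × √(2/50) = 2.4, 3.2 and 4.0 points for SD 6, 8 and 10. The false-positive rate with no true effect comes from the noncentral t with 98 df and noncentrality bias/(SD × √(2/50)). At SD 8 it is 5.2% and 5.5% for the two biases in B, and 7.9% for 0.8 points in C (6.8% at SD 10, 10.1% at SD 6).

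**The case against.** Much of the conflict can be read away. Random enrolment is the only operational step described, Patient risk speaks of both arms, and the groups are equal. The delivery sentence follows the random step and can be taken as discretion within the assigned technique. The list of RSI aspects left to the clinician does not name suction. The illustrative biases are small, and this is a pilot.

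These points stand in part. They make randomisation the likelier reading, but other wording points the other way: suction applied by convention, no new intervention, *cohorts*, and a convenience sample. Groups of 50 would also fit quota filling. Even if randomisation is granted, there is no adherence rule and the compared groups remain undefined.

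A reader might infer more than the documents support, in four ways.

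- *That the pilot is simply non-randomised.* The text leans the other way.
- *That false positives reach 18% at SD 8, or 28% at SD 6.* Those rates need the extreme corner of the assumed grid (30% prevalence, 80% versus 40% choice, a 5-point effect), and the soiled-airway exclusion removes the most obvious indication.
- *That analysis by assignment guarantees no bias.* No sequence generation or concealment is described, and the soiled-airway judgement could be made after allocation is known.
- *That provider habit could never be adjusted for.* Provider is not in the main-text list, but that list may not be exhaustive, and Appendix 3 might record provider, or assigned and delivered suction separately. An appendix form would still be unlikely to say which grouping the test uses.

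**Conclusion.** The point holds as an unresolved conflict in the rule for technique, together with an undefined primary comparison. Under the likelier reading the main cost is dilution: about 71, 61 or 50% power in place of an assumed 80%, and a difference 10, 20 or 30% too small, if that share of the continuous arm receives as-needed suction. Grouping by suction received adds little, about 0.2 to 0.3 points with a near-nominal error rate. If discretion governs, the central bias is about 0.8 points, modest against a half-width of 3.2. Every one of these figures rests on assumed inputs.

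It should be settled before enrolment because the primary comparison is undefined, not because the illustrative bias is large. If sites follow different rules, the outcome data alone could not separate the resulting shift from chance.

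**What to change.** 1. Intervention: make random assignment the only rule for choice of technique, and delete the discretion wording for that choice.
2. Intervention: require the assigned technique to be delivered by the protocol's own definitions, with clinician discretion only within that technique and for rescue suction.
3. Study Participants: judge the soiled-airway exclusion before the allocation is revealed, and conceal the allocation until then.
4. Statistical Analysis: state that the primary comparison includes all randomised patients by assigned group.
5. Data collection: record assigned and delivered suction as separate items, unless Appendix 3 already does, and report adherence by arm.

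**Cost.** A few sentences, at most one extra recorded item, and a working allocation procedure at all four sites; no extra patients. The as-assigned estimate may be smaller than an as-received one. The no-new-intervention statements in Intervention, and the claims in Patient risk about no direct impact on care and about waiver of consent, must be checked against a technique that is now assigned.
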